9.2 Data Collection

All data collection and study procedure requirements are described at the subject visits in **Section 9.1**.

9.3 Subject Consent

Informed Consent will be obtained in accordance with the Code of Federal Regulations (CFR) Title 21, Part 50. Prior to entry into the study, the California Experimental Subject's Bill of Rights (if applicable), the Institutional Review Board (IRB) and Medtronic approved ICF form and an Authorization Form required by the Health Insurance Portability and Accountability Act (HIPAA) will be presented to each subject to review and sign as applicable. The subject will be given ample time and offered the opportunity to review these documents away from the investigational center.

The following will be provided to or explained to the subject by the investigator or designee: the purpose and duration of the study, the requirements expected to be adhered to by the subject during the study and the potential risks /potential benefits associated with participation in the study. Every attempt will be made to answer the subject's questions during the informed consent process. The language used shall be as non-technical as possible and must be understandable to the subject.

Neither the investigator, nor the investigation center staff shall coerce or unduly influence a subject to participate or to continue to participate in the clinical study. The informed consent process shall not waive or appear to waive the subject's rights.

Subjects will complete California Experimental Subject's Bill of Rights (if applicable), the HIPAA Form, and the ICF. The consenting process must be documented in the subject's source documents. The subject will receive copies of the fully executed documents. A subject's participation in study procedures cannot begin before the consent process has been properly executed. When the subject decides to participate in the study, the ICF must be signed and personally dated by the subject and investigator or authorized designee, as required by the ICF. A patient contact card will be provided to the subject.

Medtronic will inform the investigators whenever information becomes available that may be relevant to the subject's confirmed participation in the clinical study. The investigator or his/her authorized designee should inform the subject in a timely manner.

Medtronic will revise the written ICF whenever new information becomes available that may be relevant to the subject's confirmed participation in the clinical study. The revised information will be sent to the investigator for approval by the IRB. After approval by the IRB, a copy of this information must be provided to the participating subjects, and the informed consent process as described above needs to be repeated.

If the ICF is amended during the course of the study, the IRB will determine:

- Whether or not active subjects should be re-consented at their next visit and

- Whether or not subjects who have completed the study at the time of the amendment should be re-consented.

Subjects will be informed that qualified personnel from the investigational center, the sponsor (Medtronic), regulatory authorities such as the FDA and/or the IRB, may have access to the clinic records that reveal their identity and health care information.

The investigational center must report the following informed consent violations to their IRB and sponsor:

- Failure to obtain informed consent from subject.
- Failure to obtain informed consent prior to performing one or more study procedures.
- Failure to maintain ICFs forms on file for all subjects who have provided informed consent.
- Use of an ICF form that has not received approval from the IRB.
- Use of an incorrect version of the ICF form.

9.4 Safety Monitoring/Risk Analysis

9.4.1 Glucose Monitoring Risk

- Subjects will be instructed to make sure they have clean fingers when performing fingerstick glucose testing.
- Subjects will have training on diabetes self-management principles.

9.4.2 Hypoglycemic/Hyperglycemic Risk

Intervention and treatment for hypoglycemia and hyperglycemia is addressed in **Section 10**.

9.4.3 Calibration of CGM Risk

When an erroneous blood glucose value is entered, which then calibrates the CGM, it can result in an inaccurate SG value. Subjects will be trained accordingly.

9.4.4 Reuse Risk

All study devices will be single patient use.

9.4.5 Sterilization Risk

The following devices will be supplied sterilized:

- Infusion sets
- Insulin reservoirs
- Sensors

9.4.6 Misuse Risk

Comprehensive training will take place at the initiation visit for investigational center staff regarding the operation of the 780G system, to include all of its functional components and all other study devices to be used during the study at the investigational center.

9.4.7 Risk of Blood Sample Collection, Contamination from Sampling Techniques

Detailed mitigations to blood sampling risk are provided in **Section 10**.

9.4.8 HbA1c Risk

A Central laboratory will be used for HbA1c testing.

9.4.9 Risks Associated with Rapid Weight Loss

Subjects who undergo a weight loss regimen that includes GLP-1 and other drugs may be subject to glycemic variability. Investigators should use their discretion to make sure that any such regimen is stable and does not cause additional risk to study subjects.

9.4.10 Transition of Subjects on MDI Therapy To/From Pump Therapy

To assist subjects who enter the study on MDI therapy, investigators and their staff will be instructed on best practices regarding the safe transition from MDI therapy to pump use at the start of the study and a safe transition back to MDI therapy at the end of the study.

For subjects transitioning from MDI to Pump:

- Consider reducing MDI total daily dose by 25% to calculate pump total daily dose before calculating pump settings
- Consider instructing subjects not to administer their long-acting insulin dose the night before/morning of the scheduled pump start.
 - If pump therapy is initiated within 24-36 hours of the last long-acting insulin injection (depending on the duration of action of the brand administered), consider setting a temporary basal rate of 0% to run until that time has passed

For subjects transitioning back to MDI therapy after study participation ends:

- Consider recalculating injection doses based on pump settings, or returning to that subject's previous MDI dose schedule and adjust as needed

9.4.11 Risk Associated with Non-Insulin Anti-Diabetic Medications

If, during the study period with AHCL therapy, the time below 70 mg/dL exceeds 4% for individual study subjects, investigator should use their clinical discretion and also consider changing pump settings. In addition to changing pump settings, investigators might also consider dose reductions or stopping the use of one or both of these two classes of medications (sulfonylureas &/or meglitinides) for individual subjects.

9.4.12 Risk Associated with SGLT Therapy

For subjects who are currently using SGLT inhibitors, the investigational center will provide training as well as a wallet card-formatted STICH protocol. The STICH protocol warns patients who are taking SGLT inhibitors about the risks associated with this therapy relative to the occurrence of ketosis and DKA.

9.5 Glucose and Glycemia Measurements

During the course of the study, the subjects' BG levels, SG levels, HbA1c, and blood ketones will be collected using the methods outlined in this section.

9.5.1 Daily Blood Glucose

Values will be assessed during the study by all subjects using the Accu-Chek Guide Link study meter. The control solution test will be performed following the manufacturer's user guide. Subjects will be trained on the use of the Accu-Chek Guide Link study meter per the manufacturer's instructions.

9.5.2 Blood Ketone Values

Blood ketones will be measured by all subjects using a ketone meter when:

- the subject is symptomatic for high blood glucose or
- the sensor glucose is >300 mg/dL, the BG should be checked by fingerstick, if BG is >300 mg/dL, blood ketones should be checked

The control solution test will be performed following the manufacturer's user guide. The investigational center staff will be trained on the use of the ketone meter per the manufacturer's instructions. All ketone measurements will be reported by study subjects.

9.5.3 Sensor Glucose Values

SG data will be collected by subject's study pump and calibrated by each subject's Accu-Chek Guide Link study meter.

9.5.4 HbA1c

HbA1c is collected at baseline and the end of subjects' participation; if subjects have completed Visit 9 and exit early, labs will be collected. In the continued access period, HbA1c were collected every 90 days.

9.6 Recording Data

Data, except questionnaires, entered by the investigational center staff will be captured on eCRFs using the Electronic Data Capture (EDC) system. Original eCRFs will not be considered as source data and supporting documentation will be required. In addition, the subject will complete the questionnaires online via direct entry. In case the online link is unavailable, subjects will complete the questionnaire using a paper format (this will be source data) and subsequently the investigator or designated investigational center staff will enter the responses online. If paper format is used, the investigator or designated investigational center staff should maintain the original paper source in the subject's source file.

Electronic device data will be collected from the study pump using CareLink Personal/CareLink system software. The system uses TLS technology, which encrypts all data it stores (21 CFR Part 11 compliant). Certain data points stored in the downloaded information may also be captured on the appropriate eCRF. Electronic device data could also be collected by the MiniMed Clinical/MiniMed Mobile app and the CareLink Clinical app.

The investigator will ensure that all eCRFs are completed promptly, completely, and accurately. Medtronic will provide detailed instructions to assist with eCRF completion. In the event of data discrepancies, investigational centers will be asked to resolve queries electronically in the EDC system; otherwise, irresolvable data-related issues will be routed to the sponsor for review and final

disposition. An audit trail is maintained in the EDC system to capture any corrections or changes of the eCRFs. System backups for data stored in the EDC system will be consistent with Medtronic SOPs.

Medtronic will only consider eCRFs to be complete when all discrepancies between source data and eCRF have been resolved. eCRF content will be reviewed by a study monitor, as described in the Monitoring Plan. In addition, specific eCRFs must also be reviewed and electronically signed by the investigator, indicating his/her agreement with the accuracy of all recorded data. It is expected that the investigator and his/her staff will cooperate with the monitoring team and provide any missing data in a timely manner.

9.7 Deviation Handling

A deviation is any instance(s) of failure to follow, intentionally or unintentionally, the requirements of the CIP. It is expected that the investigator will conduct this clinical trial in compliance with the CIP and all applicable regulations governing the conduct of clinical research involving human subjects. Failure to do so could result in one or all of the following:

- Investigational center disqualification
- Notification to the regulatory authorities/IRB depending on the severity of the deviation and reporting requirements

The investigator should not implement any deviation from, or changes to, the CIP without agreement by the sponsor and prior review and documented approval/favorable opinion from the regulatory authority (if applicable) or IRB, except where necessary to eliminate an immediate hazard(s) to trial subjects. The use of waivers from the CIP are prohibited in this study.

If there is a documented safety reason that would not permit the use of CIP defined Auto Basal target setting and Active Insulin Time settings, then use of the alternative settings will not be considered a deviation.

9.7.1 Documenting Requirements for Study Deviations

9.7.1.1 Unplanned CIP Deviations

The investigator may encounter the need to deviate from the CIP when necessary to protect the safety, rights or well-being of a subject in an emergency or in unforeseen situations beyond the investigator's control (e.g., subject failure to attend scheduled follow-up visits, inadvertent loss of data due to computer malfunction, inability to perform required procedures due to subject illness).

Deviations from the CIP, regardless of the reason should be documented as soon as possible, after the deviation occurs or is identified. This documentation should include deviation date, description of the deviation, the reason for deviation, and the corrective action. Refer to **Table 5** for reporting timelines for emergency deviations.

CIP deviations should be reported as follows:

- a) To the IRB for notification/acknowledgement;
- b) To the sponsor and, if required;
- c) To the applicable regulatory authority (reported by sponsor).

9.7.2 Reporting Requirements for Study Deviations

All study deviations must be reported on the eCRF regardless of whether medically justifiable, an inadvertent occurrence, or taken to protect the subject in an emergency. The date, description, and reason for each deviation will be documented (21 CFR 812.140 Records).

The following examples are deviations that could impact subject safety, affect the integrity of study data and/or affect subject's willingness to participate in the study. These deviations are significant and require immediate sponsor notification upon investigator awareness.:

- Failure to obtain informed consent, i.e., there is no documentation of consenting
- Informed consent obtained after initiation of study procedures
- Continuation of a subject who did not meet all inclusion/exclusion criteria
- Performing study procedure not approved by the IRB
- Failure to inform IRB and sponsor of reportable AEs (see **Section 11**)
- Investigational study device dispensed without obtaining informed consent

In the event the deviation involves a failure to obtain a subject's consent, or is made to protect the life or physical well-being of a subject in an emergency, the deviation must be reported to the IRB as well as Medtronic within five (5) working days.

Reporting of all other study deviations should comply with:

- IRB policies and/or
- local laws and/or
- regulatory authority requirements

They must be reported to Medtronic as soon as possible upon the center becoming aware of the deviation. Refer to Investigator Reports, **Table 5**, for specific deviation reporting requirements and timeframes for reporting to Medtronic, IRB, and regulatory authority (if applicable).

9.7.3 Analyzing Deviations

Medtronic is responsible for reviewing deviations, assessing their significance, and identifying any additional corrective and/or preventive actions (e.g., amend the CIP, conduct additional training, terminate the investigation). Repetitive or serious investigator compliance issues may result in initiation of a corrective action plan with the investigator and investigational center, and in some cases, necessitate suspending enrollment until the problem is resolved or ultimately terminating the investigator's participation in the study.

9.8 Subject Exit, Withdrawal or Discontinuation

Subjects may choose to withdraw from the study at any time by notifying investigational center staff of their intent.

If a subject chooses to end his or her study participation or if the subject is removed from the study at the Investigator's discretion or for failure to meet the study requirements, the reason for

withdrawal must be documented. All study devices and supplies must be returned (as applicable) and documented both in source documents and on an eCRF. Following study exit, subjects will receive standard medical care from their own providers.

A subject will be withdrawn from the study if:

- In the opinion of the investigator, the subject's health or safety would be compromised by continuing in the study (e.g., infection at skin site, severe skin reaction to adhesive).
- In the opinion of the investigator, it is in the subject's best interest to discontinue participation in the study.
- During the course of the study, subject begins using hydroxyurea.
- During the course of the study, subject uses insulin that is not allowed to be used in the study. The only permitted insulins are Humalog, Novolog/NovoRapid and Admelog.
- During the course of the study, subject begins participation in another investigational study (drug or device).
- At the discretion of the investigator: during the study it becomes known that subjects are repeatedly using a non-linked BG meter for SMBG or a system that replaces SMBG.
- During the course of the study, subject begins abusing illicit drugs.
- During the course of the study, subject begins abusing marijuana.
- During the course of the study, subject begins abusing prescription drugs.
- During the course of the study, subject begins abusing alcohol.
- During the course of the study, subject receives red blood cell transfusion or erythropoietin.
- During the course of the study, the subject demonstrates that he/she is not able to comprehend instructions for study procedures, as evaluated by the appropriate research staff.
- During the run-in period, a subject repeatedly activates SmartGuard feature when instructed otherwise, e.g., SmartGuard feature is turned on (as applicable at the discretion of the investigator).
- During the course of the study, subject is taking oral, injectable, or IV glucocorticoids. (Note: Intra-articular injections to treat pain (e.g., joint pain, bursitis, etc.) are permitted.)
 - Exception: During the continued access period in Phase 1 of the study, subjects will be allowed to receive orally administered steroid treatments for a maximum of 2 weeks. Intra-articular injections to treat pain (e.g., joint pain, bursitis, etc.) continue to be permitted. Duration of use as well as type of steroid used must be documented on the Concomitant Medications CRF.
- During the study, (female) subject becomes pregnant.
- During the study, the subject experiences one severe hypoglycemic episode, if it is related to the use of MiniMed 780G system SmartGuard feature.
- During the study, the subject experiences one episode of DKA or HHS, if it is related to the use of MiniMed 780G system SmartGuard feature.
- During the study, subject has a cardiovascular event or any vascular event such as stroke.

Documentation of the reason(s) leading to subject withdrawal will be kept in the subject's source documentation.

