8.2 Subject Enrollment

Subjects will be considered enrolled in the study upon signing the ICF.

A subject will be assigned a unique study subject ID via the eCRF, which is a 9-digit code (341XXXXXX). The first three digits refer to the CIP number (341), the next three digits refer to the investigational center number, and the last 3 digits refer to the subject number assigned during Visit 1 (e.g., 341002001 is subject 001 from investigational center 002).

The investigator will maintain a log of all subjects enrolled in the clinical study, assigning a subject ID linked to their names, and alternative subject ID.

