9.1 Schedule of Events

Subjects may participate in 2 phases.

Phase 1 (Completed): Subjects participated in a minimum of 18 planned study visits, as presented in **Section 18.4.3**, for approximately 135 days of device wear. Subjects were allowed to enter a continued access period, following the end of the study period. Phase 1 has been completed. For detailed information, see **Section 18.4 Appendix 4: Phase 1**.

Phase 2: Subjects will participate in a minimum of 18 planned study visits, as presented below in **Figure 6**, for approximately 135 days of device wear.

Virtual office visit (audio visual) may be performed for office visits in cases where an office visit is not possible. The exit visit should occur at the office unless an emergent situation occurs.

If the subject visits the investigational center outside of the scheduled study visits, a Visit eCRF will be completed to document the reason for the unscheduled visit.

If subject exits the study early (i.e., before their last scheduled visit), HbA1c requirements that apply to the final visit will be completed for subjects who have completed Visit 9. Refer to CIP341 Questionnaire Guide for collection of early exit survey/questionnaire requirements.

[figure not shown]
The Exit eCRF and all associated activities should be completed for all subjects who have withdrawn, discontinued, or completed the study.

Subjects who transitioned from Phase 1 to Phase 2:

Phase 1 subjects were given the opportunity to transition into Phase 2 upon completion of the Phase 1 study period or at a subsequent continued access period visit. Transitioning subjects were expected to complete all required Visit 1 – Phase 2 activities prior to entering Visit 9 – Phase did not need to complete Visit 2 through Visit 8 of Phase 2.

Refer to **Section 9.1.1, Table 3** for the Visit Details.

Figure 6. Phase 2 Visit Schedule

Note: Phase 1 subjects were given the opportunity to transition into Phase 2 upon completion of Phase 1 – Study Period or at a subsequent continued access period visit. Phase 1 is now complete and the Phase 1 visit schedule is presented in **Section 18.4.2** for reference.

9.1.1 Study Visit Schedule & Scheduled Follow-Up Visit Windows**Visit 1 to Visit 8 should be completed within 45 days.**

- Visit 1 (Office): Consent and screening
 - Collect labs

Run-In Period:

- Visit 2 (Office): Start Run-In
 - Eligibility has been confirmed
 - Start study pump and CGM in Manual Mode

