Train subjects on the use of the 780G BLE 2.0 insulin pump with DS5		X										
Start study subjects on the 780G BLE 2.0 insulin pump system (Manual Mode)		X										
Provide study subjects the Medtronic infusion sets, reservoirs, sensors and transmitter		X				As needed	As needed			As needed	As needed	As needed
Train subjects on the Medtronic infusion sets, reservoirs, sensors and transmitter		X										
Start study subjects on CGM (transmitter and sensor) and accessories		X										
Instruct subjects to place the sensor in a location that is approved for placement per the User guide and study directions, as applicable		X	X	X	X	X	X	X	X	X	X	If applicable
Train study subjects on the 780G BLE 2.0 SmartGuard features.							X					
Instruct subjects on the SmartGuard feature of the pump as well as specific considerations regarding SmartGuard: 
 Ensure that the Auto Correction feature is turned ON and remains ON throughout the course of the study. 							X					
Instruct subjects to switch from pump therapy to manual injections until issue is resolved if:												

CIP341 Clinical Investigation Plan

D00591227

Revision F

Page 55 of 125

Medtronic

	Visit 1 (Office)	Run-In Period					Study Period					
		Visit 2 (Office)	Visit 3, 4 & 5 (Phone)	Visit 6 (Phone)	Visit 7 (Phone)	Visit 8 (Office/Virtual Office)	Visit 9 (Office)	Visit 10 & 11 (Phone)	Visit 12, 13 & 14 (Phone)	Visit 15 & 16 (Office/Virtual Office)	Visit 17 (Office/Virtual Office)	Visit 18* (Office)
Visit Window	Enrollment		Day 1, 3 (-1 day), and 5 (-1 day) after Visit 2	Day 7 (-1 day, +2 days) after Visit 2	Day 14 (±2 days) after Visit 2	Day 21 (±3 days) after Visit 2	Day 7 (+7 days) after Visit 8	Day 2 (-1 day) and 4 (-1 day) after Visit 9	Day 7 (±2 days), 14 (±3 days), and 21 (±3 days) after Visit 9	Day 30 (±3 days) and 44 (±3 days) after Visit 9	Day 60 (±7 days) after Visit 9	Day 90 (±7 days) after Visit 9 End of Study

Hospital admission is needed for any reasonGlucose is persistently elevated (i.e., above 300 mg/dL) and not responding to correction boluses and/or infusion set change(s).There is an occlusion alarm with elevated glucose, where the study subject is not able to address the occlusion by changing the infusion set												
Adjust pump settings		X	As needed	As needed	As needed	As needed	X	As needed	As needed	As needed	As needed	As needed

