11.2 Definitions and Classification of Adverse Events

Medtronic uses the definitions provided in ISO 14155:2020 and 21 CFR 812 for AE definitions. Where the definition indicates "device", it refers to any device used in the study. This might be the device under investigation, or any market released component of the system.

Severe Hypoglycemia is an event requiring assistance of another person due to altered consciousness to actively administer carbohydrate, glucagon, or other resuscitative actions.^[5]

This means that the subject was impaired cognitively to the point that he/she was unable to treat himself or herself, was unable to verbalize his or her needs, and was incoherent, disoriented and/or combative.

These episodes may be associated with sufficient neuroglycopenia to induce seizure or coma. Plasma glucose measurements may not be available during such an event, but neurological recovery attributable to the restoration of plasma glucose to normal is considered sufficient evidence that the event was induced by a low plasma glucose concentration. ^[5]

Severe Hyperglycemia is defined as hyperglycemia (BG greater than [$>$] 300 mg/dL) with BG ketones greater than ($>$) 1.5 mmol/L, and/or accompanied by symptoms of nausea, vomiting or abdominal pain.

The meter and ketone test strips are supplied for the evaluation of ketone monitoring. Only blood ketones will be recognized (not urine ketones) for assisting in diagnosis of severe hyperglycemia. The monitors/test strips are quality controlled prior to dispensing to subjects. Blood ketones provide contemporaneous understanding of ketone levels associated with elevations in glucose.

Diabetic Ketoacidosis/DKA diagnostic criteria: BG greater than ($>$) 250 mg/dL, arterial pH less than ($<$) 7.3, bicarbonate less than ($<$) 15 mEq/L, moderate ketonuria or ketonemia and requiring treatment within a health care facility.^[6]

Hyperglycemic events will be recorded as DKA if the event includes the presence of all of the following:

- Arterial blood pH less than ($<$) 7.30 or serum bicarbonate less than ($<$) 15 mEq/L
- Blood glucose greater than ($>$) 250 mg/dL
- Serum ketones or large/moderate urine ketones
- Symptoms such as polyuria, polydipsia, nausea, or vomiting
- Treatment provided in a health care facility

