1. Was the severe hypoglycemia, HHS or DKA related to the AHCL algorithm, or was it related to a known insulin pump risk? For example, a question that may be considered in HHS or DKA would be whether the event was related to an infusion set issue or caused by the AHCL algorithm.
2. Another important consideration would be if the severe hypoglycemia, severe hyperglycemia, HHS or DKA event was related to a device malfunction versus patient non-compliance. For example, if a software anomaly leading to an under-delivery of insulin is discovered versus the subject repeatedly ignoring alarms prompting the subject to take action.

3. Severe hypoglycemia, severe hyperglycemia, HHS or DKA caused directly by an infusion set issue when the study pump is functioning as intended would likely result in acceptance to proceed with the study versus severe hypoglycemia, HHS or DKA that are directly caused by the AHCL algorithm or a device malfunction might stop study enrollment or entire study altogether.
4. It should be noted that the final determination of causality related to 780G system that is made by the CEC may include additional factors which the members consider to be clinically relevant and important.

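### Section 9.8 requires withdrawal for any use of a non-permitted insulin, with no exemption for insulin given in a health care facility, although Table 3 treats hospital admission as a temporary pause from the pump

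*Protocol*

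**What the plan says.** The Section 9.8 list states when a subject will be withdrawn. One trigger is that "During the course of the study, subject uses insulin that is not allowed to be used in the study", followed by the three permitted rapid-acting analogues. Other bullets in the list are qualified. Use of a non-linked meter must be repeated and is left to the investigator. Activating SmartGuard during run-in must also be repeated. Glucocorticoids carry a written exception for Phase 1 continued access. DKA or HHS counts only when "the subject experiences one episode of DKA or HHS, if it is related to the use of MiniMed 780G system SmartGuard feature". The insulin bullet has nothing comparable, and Section 9.7 prohibits waivers.

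Table 3 (Section 9.1.1) tells sites to "Instruct subjects to switch from pump therapy to manual injections until issue is resolved if" one of three conditions arises: hospital admission for any reason, persistent glucose above 300 mg/dL that does not respond to correction, or an occlusion the subject cannot clear. It does not name the insulin to inject.

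SAP Section 7.3 takes all effectiveness endpoints from data between Visit 16 and the end of the study period. SAP Section 7.1.4 puts everyone who starts the study period in ITT and restricts the per-protocol set to subjects who complete it.

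**The concern.** A subject in hospital often does not choose the insulin. Table 3 plans for that subject to return to the pump once the problem is over. Section 9.8 ends participation if the facility gives anything outside the three analogues, for however short a time. Whether the subject stays then depends on the facility's choice of insulin rather than on device safety or the subject's willingness to continue.

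This loss follows a health event, so it may be informative, and it is avoidable. An exit between Visit 9 and Visit 16 leaves an ITT subject with no primary effectiveness data. An exit at any time in the study period removes the subject from the per-protocol set and ends follow-up early.

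A smaller point is that the bullet does not say when it begins to apply.

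**Working it through.** **The rules side by side.**

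1. *Admission, permitted analogue injected.* Table 3 is followed and the 9.8 insulin bullet is not triggered. There is no conflict.
2. *Admission, another insulin given, and another exit rule also applies* (cardiovascular event, transfusion, glucocorticoids, or SmartGuard-related DKA, HHS or severe hypoglycemia). The subject exits anyway, so the insulin bullet adds nothing.
3. *Admission, another insulin given, no other exit rule applies.* Table 3 foresees a return to the pump, but 9.8 requires exit. DKA caused by an infusion set fault is an example. Section 11.2 includes "Treatment provided in a health care facility" among the criteria for DKA and for HHS, so facility insulin is likely, while the DKA/HHS bullet itself applies only to SmartGuard-related events.

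The emergency clause in Section 9.7 excuses a deviation made to remove an immediate hazard. It does not say that the subject may then remain in the study.

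**When the bullet starts.** Section 8.2 says "Subjects will be considered enrolled in the study upon signing the ICF", and MDI entrants arrive on long-acting insulin (Section 8.3, criterion 3). Section 9.1.1 says "Visit 1 to Visit 8 should be completed within 45 days", with Visit 8 on Day 21 (±3) after Visit 2. Consent to pump start can therefore take up to 45 − 21 = 24 days (45 − 24 = 21 to 45 − 18 = 27). Section 9.4.10 advises sites: "Consider instructing subjects not to administer their long-acting insulin dose the night before/morning of the scheduled pump start". Long-acting use until about then is thus expected. The Table 3 row listing permitted insulins is blank at Visit 1 and starts at Visit 2. The intended start is pump start, but 9.8 does not say so.

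**Timing (from the schedule).** Visit 16 is Day 44 and Visit 18 is Day 90.
- Share of evenly timed study-period exits before Visit 16: 44/90 = 0.489 (41/97 = 0.423 to 47/83 = 0.566 across visit windows).
- Length of the effectiveness window: 90 − 44 = 46 days (83 − 47 = 36 to 97 − 41 = 56).

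**Size (illustration; every rate is assumed).** The documents give no admission rate, so take 300 subjects entering the study period, 1–5% admitted, 25–50% of those exiting under another rule, and 50–100% of the rest given a non-permitted insulin.
- Exits due to this bullet alone: low 0.01 × 0.50 × 0.50 = 0.0025 (0.75 subjects); high 0.05 × 0.75 × 1.00 = 0.0375 (11.25 subjects).
- Before Visit 16: × 0.489 = 0.0012 to 0.0183 (0.37 to 5.5 subjects).
- Shift in mean TIR = proportion missing × difference in TIR. With an assumed difference of 0–20 points in either direction, the maximum is 0.0183 × 20 = 0.37 points, and 0.37/7.5 = 4.9% of the margin.
- Standard error at n = 300 for an assumed SD of 12, 15 or 18: 0.69, 0.87 or 1.04. The maximum shift is 0.53, 0.42 or 0.35 standard errors.
- Follow-up lost at an average of 45 days per exit: 34 to 506 of 300 × 90 = 27,000 subject-days (0.1% to 1.9%).

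**The case against.** The strongest reply is that nothing here is a formal contradiction. Table 3 instructs subjects to stop the pump and inject; it names no insulin and makes no promise of retention. A permitted analogue satisfies both rules. The exit criteria are independent, so escaping one does not protect against another. Strictness also has a safety reason: Table 4 lists hypoglycemia from injected insulin while in closed loop. And the effect is small on any plausible figures. All of this stands, and it limits the point to the third case above.

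A reader might infer more, and the documents do not support it:

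- *That the bullet cannot be applied as written, because it would remove MDI entrants taking basal insulin after consent.* The Visit 2 start of the Table 3 row, the admission of MDI users and the handling of residual long-acting insulin in Section 9.4.10 show that pump start is meant. What remains is a missing phrase. Subjects lost before Visit 9 never enter ITT, so they cannot cause the missing TIR.
- *That Section 12.1 means subjects with infusion set failures should stay in.* The Clinical Events Committee is asked "whether the event was related to an infusion set issue or caused by the AHCL algorithm", but that passage concerns whether the study proceeds, not whether an individual is retained.
- *That safety information is lost at exit.* The Table 3 footnote applies all Visit 18 requirements to early exits in the study period, including adverse event questions and HbA1c. Only observation after exit is lost.
- *That early-exit HbA1c has no analysis rule.* Parts of the SAP are blacked out, so silence in the visible text does not show a gap.

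**Conclusion.** The point holds in a limited form. A subject given a non-permitted insulin in a health care facility must leave even when no other exit rule applies and Table 3 expects a return to the pump. If this happens before Visit 16, the subject counts in ITT without primary effectiveness data. The start of the rule at pump start is clear from context but not stated.

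The frequency cannot be derived from the documents. The 0.37-point upper figure rests on assumed admission, overlap and hospital-insulin rates, evenly timed exits, and a 20-point TIR difference of unknown direction. It would be tempting to infer that the primary result is at risk, but neither the documents nor this illustration supports that. The reason to change the rule is that it causes avoidable, health-related loss of follow-up that a short exemption would prevent.

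**What to change.** Reword the Section 9.8 bullet so that it covers a non-permitted insulin used in the study pump, or used after pump start outside a health care facility. Exempt insulin given in a health care facility. State that exempted subjects remain in follow-up through Visit 18 with their HbA1c and available sensor data in ITT.

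In Table 3, say that injections outside a facility should use a permitted analogue where possible, and that SmartGuard resumes only when the investigator judges that the injected insulin has cleared. The 0% temporary basal in Section 9.4.10 covers initial pump start only, so re-entry needs its own sentence. The insulin, dates and reason can be recorded under the existing Table 3 item for diabetes medication changes.

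The cost is a few sentences through the amendment route in Section 16.7, with no new forms or visits. Mean TIR and HbA1c may be slightly less favorable because these subjects stay in. The clearance judgment carries the hypoglycemia risk listed in Table 4. The first two Section 9.8 bullets still let the investigator withdraw anyone whose safety or best interest requires it.
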